3.1 Characteristics

We will prospectively enroll four hundred HIV-positive women to undergo cervical cancer screening at FACES-supported MOH clinics in Kisumu County. After informed consent, clinical and demographic information will be collected, and participants will undergo cervical cancer screening using HPV testing. Women who previously screened positive for HPV (within the last 3 months) but have not undergone treatment will also be eligible for recruitment. Women with a positive HPV test will be evaluated for treatment with thermal coagulation, per WHO standards of ablative treatment. Per the WHO and Kenya Ministry of Health guidelines, women who will be candidates for thermal coagulation if the squamocolumnar junction is fully visualized, the cervical lesion covers less than 75% of the cervix, and there is no endocervical component or suspicion of cancer.⁸ Women who are not candidates for ablation will be referred to nearby a referral facility. All participants with a positive HPV test will undergo directed biopsy just prior to treatment for disease ascertainment but proceed to have same-day treatment, according to the WHO guidelines for screen & treat.

At 12-months after treatment, all participants treated at baseline will undergo repeat colposcopy, directed biopsy for those with cervical abnormalities or those with CIN2/3 at baseline, as well as provider collected HPV testing for persistence. Twenty-five percent of women with normal colposcopy will have a random biopsy at 6 or 12-O'Clock to confirm the absence of disease. Pain will be assessed immediately following treatment using a visual analog scale (VAS). The presence and severity of AEs will be assessed 4-6 weeks following treatment via a phone call, or in person visit, if warranted. Healthcare providers offering thermal ablation for the treatment of precancerous lesions will be surveyed at 4-6 week follow-up to evaluate provider acceptability and satisfaction with this treatment method.

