5.3 Visual Inspection with Acetic Acid

In this study, VIA will be performed on all HPV positive women to assess for eligibility for ablative treatment in a process referred to visual assessment for treatment (VAT).⁶ After identification of the cervical anatomy, including the squamocolumnar junction, the clinician will apply 5% acetic acid to the cervix. After one minute, the clinician will examine the cervix again to interpret results of the VIA according to the following criteria:

VIA will be defined as negative if the following findings are present:²⁶

1. Circumferential identification of the squamocolumnar junction (SCJ)
2. No aceto-white or faint, ill-defined white lesions at the SCJ or aceto-white lesions far away from the SCJ

VIA will be defined as positive if the following findings are present, as established by the International Agency for Research on Cancer (IARC):^{8,26}

1. Raised, thickened, a well-defined, opaque aceto-white lesion at or close to the SCJ
2. Large circumferential aceto-white lesions covering the external os
3. Pre-existing condyloma or leukoplakia which turns intensely white after application of acetic acid

The WHO criteria for cryotherapy will be used to assess for eligibility for thermal coagulation – namely, if the squamocolumnar junction is fully visualized, the cervical lesion covers less than 75% of the cervix, and there is no endocervical component or suspicion of cancer.⁴ These criteria for the use of thermal coagulation widely accepted and is used in other studies and clinical settings.

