5.7.2 Provider Acceptability Evaluation

At 4-6 week follow up, providers will be surveyed using a Provider Acceptability survey, modified from the System Usability Scale to evaluate provider acceptability and satisfaction with the use of thermal coagulation for treatment of precancerous lesions.³²

5.8 12 Month Follow-up Exam

At approximately 12-months after treatment, all participants treated at baseline will undergo repeat colposcopy, biopsy for those with CIN2/3 at baseline or those with suspicious lesions on colposcopy, as well as provider collected HPV-collection for persistence. Twenty-five percent of women with normal colposcopy will have a random biopsy at 6 or 12-O'Clock for ascertainment and avoidance of verification bias.

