7.1 Primary Objective

To evaluate the efficacy of thermal coagulation for the treatment of HIV-positive, HPV-positive women by assessing rates of HPV persistence and CIN2/3 at 12 months after treatment

Four hundred HIV-positive women with positive HPV testing will undergo colposcopy-directed biopsy for disease ascertainment prior to same-day treatment with thermal coagulation. At 12-months after treatment, all participants will undergo repeat HPV testing for persistence, and those who are HPV-positive will undergo repeat colposcopy, and biopsy as indicated for abnormal results, or random biopsy for 25% of those with normal colposcopy. We will define cure as a normal biopsy result or normal colposcopy among those who do not receive a biopsy.

Statistical Analysis: We will report the proportion of women with no evidence of cervical dysplasia at 12-months (primary outcome) follow-up, including 95% confidence intervals. We will extrapolate the rate of disease among those with normal colposcopy based on the rate of disease among the 25% in this group who will receive biopsy, and this will be incorporated in calculating persistence. We will perform a logistic regression to examine predictors of treatment success, using clinical and demographic variables as predictor variables. We will also report the rate of persistence of HPV at follow-up and compare with rates reported in the literature in this same population. We will compare efficacy rates for clearance of CIN2/3 to historical results following cryotherapy treatment in similar settings. A one-sample exact test will be used to compare the obtained efficacy proportion to that of historical controls.

We will leverage the robust infrastructure of the FACES in which patients are seen every one-to three months, and there is an established patient tracing system (including home visits) to reduce loss-to-follow-up. With a loss-to-follow-up rate of 10%, we will still be powered to answer this objective. Prior studies at this clinic have been able to achieve > 90% follow-up rate.³⁶ While limited by the lack of randomization to cryotherapy versus thermocoagulation, this study will provide pilot results that may enable a future randomized study evaluation of these two treatment methods.

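### Section 7.1 scores a woman with baseline CIN2/3 as cured on colposcopy alone when her required 12-month biopsy is missing

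*Combined protocol and SAP*

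**What the plan says.** **Cure rule (7.1).** "We will define cure as a normal biopsy result or normal colposcopy among those who do not receive a biopsy". Baseline histology plays no part in it, and there is no category for a required biopsy that was not obtained or could not be read.

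**Who is biopsied at 12 months.** Three sections answer differently:
- 3.1: "directed biopsy for those with cervical abnormalities or those with CIN2/3 at baseline".
- 5.8: "biopsy for those with CIN2/3 at baseline or those with suspicious lesions on colposcopy".
- 7.1: "those who are HPV-positive will undergo repeat colposcopy, and biopsy as indicated for abnormal results, or random biopsy for 25" percent of those with a normal colposcopy. Baseline CIN2/3 is not mentioned.

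Sections 3.1 and 5.8 give colposcopy to all treated women; 7.1 gives it only to those who are HPV-positive at 12 months.

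**Planned correction (7.1).** "We will extrapolate the rate of disease among those with normal colposcopy based on the rate of disease among the 25% in this group", and "this will be incorporated in calculating persistence". Section 7.1 does not say how the result enters the cure proportion or the one-sample exact test, or whether it is done separately by baseline disease.

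**Test population (3.3).** Non-inferiority is sized on 140 women with CIN2/3, with cryotherapy efficacy of 77.2%, a margin of 10 points and a one-sided level of 0.025.

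**The concern.** Sections 3.1 and 5.8 do not rely on colposcopy alone for a woman with baseline CIN2/3: they have her biopsied whatever it shows. The scoring rule in 7.1 does not carry this over. If her biopsy is refused or not done, she falls among the women without a biopsy, and a normal colposcopy makes her a cure although her disease status is unverified. For an unreadable specimen the rule gives no answer at all.

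The error runs in one direction, towards cure, and it falls in the group on which the non-inferiority conclusion rests. The study rationale (1.4) presents biopsy verification at 12 months as a main strength, and the outcome rule does not enforce it.

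**Working it through.** **1. Inputs from the plan (3.3).** Boundary = 77.2% - 10 points = 67.2%. Women with CIN2/3 = 0.35 x 400 = 140. One-sided level 0.025. I take the exact test in 7.1 to be run against the 67.2% boundary, since 3.3 supplies it.

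**2. Pass mark.** This is the smallest r with P(X >= r | n = 140, p = 0.672) <= 0.025.
- P(X >= 105) = 2.83%
- P(X >= 106) = 1.80%

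The study passes with 106 or more cures, and the false-positive rate with complete biopsies is 1.8%.

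The plan gives no figure for missing biopsies. Its stated 90% power does not reproduce with this rule: the exact test gives 70.3% at a true 77.2% and 79.6% at a true 78.2% (77.2% plus the stated 0.0102). That is a separate matter and does not affect this point.

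**3. The rule applied to one woman with baseline CIN2/3 and a normal 12-month colposcopy.**

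| 12-month biopsy | 3.1 and 5.8 | Score under 7.1 |
|---|---|---|
| Taken, normal | as required | cured |
| Taken, abnormal | as required | not cured |
| Not taken | requirement not met | cured |
| Taken, unreadable | requirement not usefully met | no rule |

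The third row is the defect.

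**4. Size, with assumed inputs.** The documents give neither the share of women without a usable biopsy (m) nor the share of residual disease invisible at colposcopy (v). I assume m = 10-20% and v = 20-40%, and that women without a usable biopsy are scored on colposcopy. With true cure at the boundary:

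apparent cure = 0.672 + 0.328 x m x v

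| m | v | Rise (points) | Apparent cure | P(X >= 106) |
|---|---|---|---|---|
| none | - | 0 | 67.2% | 1.8% |
| 10% | 20% | 0.7 | 67.9% | 2.7% |
| 10% | 40% | 1.3 | 68.5% | 3.8% |
| 20% | 20% | 1.3 | 68.5% | 3.8% |
| 20% | 40% | 2.6 | 69.8% | 7.5% |

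Every scenario exceeds the planned 2.5%.

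**5. Does the 25% extrapolation remove this?** Not clearly. It is stated for persistence, not for the proportion that enters the exact test. Its rate is to come from women with normal colposcopy as a group, and about 65% of enrolled women (100% - 35%) are expected to have no baseline CIN2/3. A pooled rate need not hold for a woman with CIN2/3 whose biopsy is missing, and no split by baseline disease is planned.

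**The case against.** The strongest reply is that the procedures close this route. Sections 3.1 and 5.8 have every woman with baseline CIN2/3 biopsied, so a colposcopy-only cure in this group needs a departure from the protocol. If all of them are biopsied and biopsy decides, the bias is zero. That is correct, and it limits the size. It does not settle how the departures are scored, and 7.1, the section the analyst will follow, does not repeat the requirement.

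The second reply is that the plan recognises verification bias and provides the 25% random biopsies against it. That also stands as intent. What is missing is the link to the cure proportion and to women with baseline CIN2/3.

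Three stronger readings are tempting, and the documents do not support them.

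- **An unseen squamocolumnar junction counts as cure.** At baseline a negative visual test needs "Circumferential identification of the squamocolumnar junction (SCJ"), and ablation is allowed only "if the squamocolumnar junction is fully visualized, the cervical lesion covers less than 75% of the cervix"; nothing similar is written for 12 months. This is silence. No section calls such an examination normal, and 5.4 ties baseline colposcopy to a named guideline whose content cannot be checked here. Women with baseline CIN2/3 are also due a biopsy whatever is seen, so the route would again need a missing biopsy.
- **Most women with CIN2/3 will go unbiopsied because 7.1 says so.** With no correction, and only a quarter of normal colposcopies biopsied, apparent cure would be 0.672 + 0.328 x (1 - s) x 0.75. For an assumed colposcopy sensitivity s of 0.9 or 0.8 that is 69.7% or 72.1%, with false-positive rates of 6.9% or 19.8%. Sections 3.1 and 5.8 say otherwise, so this shows why the sections must agree, not what to expect.
- **Minor findings become failures without histology.** The biopsy trigger is worded differently in 3.1, 5.8 and 7.1, but 7.1 is close to 3.1. It is a minor inconsistency to reconcile.

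**Conclusion.** The point holds for women with baseline CIN2/3 whose 12-month biopsy is missing: 7.1 as worded scores them cured on a normal colposcopy, against the verification that 3.1 and 5.8 require. On the assumed inputs the effect is modest, 0.7 to 2.6 points of apparent cure, but enough to lift the false-positive rate from 1.8% to 2.7-7.5% against a planned 2.5%. The direction follows from the rule; the size rests entirely on the assumed shares and shrinks to nothing as biopsy completeness approaches 100%. A reader should not infer that the plan ignores verification bias, or that an inadequate examination is declared normal. The outcome rule should be corrected before the data are analysed.

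**What to change.** In 7.1:
1. For women with baseline CIN2/3, define cure as a normal, adequate 12-month biopsy. Treat a missing or inadequate biopsy as outcome unknown: not cured in the primary non-inferiority test, excluded in a named sensitivity analysis.
2. Limit the colposcopy-only route to women without baseline CIN2/3, and state how the 25% extrapolation enters their cure proportion.
3. Reconcile the 12-month work-up across 3.1, 5.8 and 7.1: who has colposcopy, what triggers a biopsy, and the place of baseline CIN2/3.

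**Cost.** Items 1 and 2 are wording changes and add no procedure beyond what 3.1 and 5.8 already require; item 3 may, depending on the trigger the sponsor settles on. The reported cure rate will be lower, slightly if few biopsies are missing and more if many are. At a true 77.2%, with biopsies missing irrespective of outcome, the scored rate is 0.772 x (1 - m): 75.7% at m = 2%, 73.3% at 5% and 69.5% at 10%. The chance of reaching 106 of 140 falls from 70.3% to 53.9%, 29.8% and 6.3%. Excluding the 10% instead leaves 126 women, a pass mark of 96 and a 65.3% chance. The primary rule is therefore protective but demanding, so biopsy completeness in this group should be tracked during follow-up and both analyses reported side by side.

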2.1 Hypothesis

We hypothesize that the efficacy of thermal coagulation for the treatment of CIN2/3 among HIV-infected women will be similar to reported rates of cryotherapy among this population.

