2.2 Primary Objective

To evaluate the efficacy of thermal coagulation for the treatment of HIV-positive, HPV-positive women by assessing rates of HPV persistence and CIN2/3 rate at 12 months after treatment

- Endpoints:
 - Proportion of women with no evidence of cervical dysplasia at 12-month follow-up based on colposcopy and biopsy.
 - Proportion of women with persistent HPV at 12-month follow-up

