3.3 Sample Size and Power Calculation

The study sample size is calculated based on the primary objective.

We seek to enroll 400 participants in order to obtain sufficient numbers of women who have CIN2/3, our outcome of interest. Based on prior studies in this population, we anticipate approximately 35% of HPV-positive women (N ~ 140) will have biopsy-proven CIN2/3.²⁴ The study design is a non-inferiority trial using results from the only study using standard cryotherapy in a similar population¹⁹ to establish the non-inferiority boundary. We

will compare the efficacy rate in our study using thermocoagulation to the non-inferiority boundary established using the efficacy rate and lower 95% confidence bound from this cryotherapy treatment publication from a similar population.¹⁹

The efficacy results of cryotherapy in the De Vuyst paper were 77.2% (95% CI: 66.4-85.9%).¹⁹ Using 77.2% with a non-inferiority margin of 10% which is at the limit of the confidence bound and is closest to the null effect.²⁴ Using this margin, the new treatment method is hypothesized to be at least as good as cryotherapy. Based on this non-inferiority margin, a sample size of 140 women with CIN2/3 achieves 90% power in using a one-sided test with a significance level of 0.025. Based on this sample size, power of 90%, and significance of 0.025, the minimal detectable effect size (the actual difference between cryotherapy and thermocoagulation) is 0.0102.

We will leverage the robust HIV-care infrastructure at FACES in which patients are seen at every one to three months, and the presence of an established patient tracing system (including home visits) to reduce loss-to-follow-up. Assuming a 14% loss to follow-up, which would result in a sample size of 120, we are still be powered for our non-inferiority margin of 10% with a minimal detectable effect size of 0.0184, with 80% power and an alpha of 0.025. Sample size and non-inferiority calculations used NCSS PASS software and G-Power software.

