4.2 Recruitment and Enrollment

Women receiving care at FACES-supported HIV- clinics will be considered for recruitment into the study. At these clinics, patients are introduced to cervical cancer screening as part of an HIV education session when they enroll in care. Information about cervical cancer and the opportunity for screening is reinforced as part of a general daily health talk given while patients are waiting to be seen for their routine HIV care, and then reinforced through individualized counseling during their clinical visit. Women willing to undergo cervical cancer screening will be screened consecutively for their study eligibility and asked about their willingness to participate in the study.

Screening and informed consent for participation in the study will take place in a private gynecologic exam room prior to a pelvic exam. Women who previously screened positive for HPV (within the last 3 months) but have not undergone treatment will also be eligible for recruitment. Those who screen positive and are eligible for thermal ablation will be offered treatment and will form the study group

Participant Registration

A written, signed, informed consent form (ICF) must be obtained before any study-specific assessments are initiated. A copy of the signed ICF will be given to the subject and a copy will be filed in the medical record. The original will be kept on file with the study records.

All participants consented to the study will be registered in OnCore®, the UCSF Helen Diller Family Comprehensive Cancer Center Clinical Trial Management System (CTMS). The system is password protected.

5 Study Procedures and Assessments

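### The primary cure proportion and the treatment-success regression are not restricted to women with CIN2/3 at baseline, and the exact test does not say which proportion it uses

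*Combined protocol and SAP*

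**What the plan says.** Women enter on a positive HPV test and are biopsied and treated on the same day, before histology is known. Section 4.2 defines the group: "Those who screen positive and are eligible for thermal ablation will be offered treatment and will form the study group". Section 7.1 opens its analysis with that group: "Four hundred HIV-positive women with positive HPV testing will undergo colposcopy-directed biopsy for disease ascertainment prior to same-day treatment with thermal coagulation".

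The endpoint in 2.2 is "Proportion of women with no evidence of cervical dysplasia at 12-month follow-up based on colposcopy and biopsy", and 7.1 repeats it as the primary outcome: "We will report the proportion of women with no evidence of cervical dysplasia at 12-months (primary outcome) follow-up, including 95% confidence intervals". Cure is defined by the 12-month findings alone: "We will define cure as a normal biopsy result or normal colposcopy among those who do not receive a biopsy". The regression carries no restriction either: "We will perform a logistic regression to examine predictors of treatment success, using clinical and demographic variables as predictor variables".

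The efficacy question is narrower. Section 2.1 hypothesises that "the efficacy of thermal coagulation for the treatment of CIN2/3 among HIV-infected women will be similar to reported rates of cryotherapy", the rationale in 1.4 concerns biopsy-proven CIN2/3, and 3.3 sizes the study on 140 women with CIN2/3 because "we anticipate approximately 35% of HPV-positive women (N ~ 140) will have biopsy-proven CIN2/3".

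Section 7.1 also plans to compare CIN2/3 clearance with historical cryotherapy results. Its next sentence applies a one-sample exact test to the efficacy proportion obtained, without naming the denominator.

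**The concern.** A woman with no lesion at baseline and a normal 12-month examination meets the definition of cure, although she had no CIN2/3 to clear. A proportion over all treated women therefore mixes absence of baseline disease with response to treatment, and a single-arm study has no control group to separate the two.

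The reference of 77.2% in 3.3 is used there as an efficacy rate for CIN2/3. Setting an all-women proportion against it, or against the boundary derived from it, would compare two different quantities. In an all-women regression, factors associated with having no disease at baseline would appear as predictors of treatment success.

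**Working it through.** **Inputs from section 3.3.** 400 HPV-positive women; 35% with CIN2/3; cryotherapy efficacy 77.2%; margin 10 points; one-sided significance level 0.025; 14% loss to follow-up.

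**The plan's own figures.** 400 × 0.35 = 140 with CIN2/3, leaving 260 (65%) without. 140 × 0.86 = 120.4, matching the stated 120. Boundary: 77.2 − 10 = 67.2%.

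**Dilution.** Let c be the share of baseline CIN2/3 that clears, and f the share of the other women who are dysplasia-free at 12 months. Then

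all-women proportion = 0.35c + 0.65f.

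The documents do not give f, so 85% to 95% is an assumption. At the boundary with f = 85%: 0.35 × 0.672 + 0.65 × 0.85 = 0.2352 + 0.5525 = 0.7877.

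**Exact test against 67.2%.** The smallest count whose one-sided binomial tail is at most 0.025 is 106 of 140 (75.7%) or 288 of 400 (72.0%).

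| c | All-women proportion, f = 85% | f = 95% | Chance of passing, 400 women (f = 85% to 95%) | Chance of passing, 140 with CIN2/3 |
|---|---|---|---|---|
| 0% | 55.25% | 61.75% | below 0.001 | 0 |
| 50% | 72.75% | 79.25% | 0.66 to above 0.99 | below 0.001 |
| 67.2% | 78.77% | 85.27% | above 0.99 | 0.018 |
| 77.2% | 82.27% | 88.77% | above 0.99 | 0.70 |

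With 14% loss, 400 × 0.86 = 344 women. The test then needs 249, and the chance of passing at c = 67.2% stays above 0.99.

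**Sensitivity to f.**
- *Upper extreme, f = 100% (no CIN1, no new disease).* No effect gives 65%, with a 0.002 chance of passing. Clearance of 20% gives 0.35 × 0.20 + 0.65 = 72%, with a chance of 0.53. Clearance of 30% gives 75.5%, with a chance of 0.95.
- *Lower f.* The endpoint is absence of any dysplasia, so persistent CIN1 counts as failure. The documents give no CIN1 share. If 10%, 20% or 30% of treated women have CIN1 that persists and the rest of the 65% stay clear, the no-effect figure is 55%, 45% or 35%. At c = 67.2% with persistent CIN1 in 20%, the proportion is 0.45 + 0.2352 = 68.52%; with 30% it is 58.52%, below the boundary.
- At c = 67.2% the all-women figure exceeds 67.2% only when f does. At f = 70% it is 0.2352 + 0.455 = 69%.

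**Regression.** At 77.2% efficacy, 120 women give 120 × 0.228 ≈ 27 failures. Section 5.9 lists about a dozen candidate predictors.

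**The case against.** The strongest reply is that the inferential comparison is already tied to CIN2/3. Section 7.1 names CIN2/3 clearance as what will be compared with cryotherapy, and the exact test in the next sentence most naturally refers to that rate. Section 3.3 says the sample size serves the primary objective and counts women with CIN2/3. Every HPV-positive woman is biopsied at baseline (5.4), so the rate can be calculated. Much of this stands: the comparison is probably meant for the CIN2/3 subset, and a reader who inferred that the plan never measures CIN2/3 clearance would be wrong. It does not settle the matter, because the outcome labelled primary, its interval and the regression carry no such restriction, and the test does not name its proportion.

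Second, no sentence says that cure is taken over all treated women. That is the natural reading, not an explicit statement. Section 7.1 is not even cleanly all-women, since it gives 12-month colposcopy only to women still HPV-positive, whereas 3.1 and 5.8 give it to all treated women.

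Third, a reader might infer that the proportion stays high even if the treatment does nothing. The figures do not support this: zero clearance gives 55-62%, or at most 65% if no other woman has dysplasia at 12 months, and fails the boundary.

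Fourth, the primary objective is worded for HPV-positive women, and a 12-month dysplasia-free proportion among all those treated is a legitimate programme outcome. That supports reporting it, under a name other than cure or efficacy.

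**Conclusion.** The concern holds in a limited form. The primary outcome, the cure definition and the regression are not restricted to baseline CIN2/3, which conflicts with the hypothesis and the sample size, and the denominator of the exact test is not named. An all-women proportion does not measure CIN2/3 cure and is not comparable with 77.2%.

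The choice of denominator can reverse the conclusion. For a treatment exactly at 67.2%, the chance of passing is 0.018 in 140 women with CIN2/3 and above 0.99 in 400 treated women. This rests on the plan's 35%, on 400 HPV-positive women, on a test against 67.2% at one-sided 0.025, and on f = 85-95%, which no document supports. If CIN1 is common and persists, the inflation shrinks or reverses, but the figure still would not measure CIN2/3 cure. The risk is that a weak or borderline treatment looks adequate; a treatment with no effect would not pass.

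**What to change.** In 2.2 and 7.1, state that the primary cure proportion, its 95% confidence interval and the exact test against the cryotherapy boundary use treated women with biopsy-proven CIN2/3 at baseline (about 120 to 140).

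Fit the treatment-success regression in those women, with few predictors because failures will be few. If it is kept in all treated women, adjust for baseline histology and do not call the outcome treatment success.

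Report the all-treated proportion separately, as the 12-month dysplasia-free prevalence among treated HPV-positive women.

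The cost is wording only, since the baseline biopsies are already planned. The downside is a wider interval. At 77.2%, the approximate half-width 1.96 × √(0.772 × 0.228 / n) is 4.1 points for n = 400, 7.0 for n = 140 and 7.5 for n = 120. The last two are sample sizes that the design already assumes.

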3.5 Risks and Benefits

3.5.1 Potential Risks

We anticipate that the potential risks to participants in the study will be minimal. Study subjects may feel discomfort or embarrassment during the pelvic exam. There may be minimal discomfort during self-collection of HPV specimens. Participants may be at risk for psychological or emotional discomfort at different stages of the study if they have a diagnosis of CIN2/3 and learn about the potential risk of cervical cancer. Participants may risk some discomfort and mild spotting after the colposcopy and biopsy. We anticipate that this will be minimal, as exams will be performed by trained clinicians, and thermal coagulation would ablate the biopsied area with the tissue desiccation, hence stopping any bleeding. Other mechanisms to achieve hemostasis at bleeding sites including use of Silver Nitrate sticks will be available to study clinicians. Women who are not eligible for thermocoagulation due to large lesions will be referred to a nearby tertiary facility for further care, per clinic protocol. Following treatment for abnormal screening, women will have vaginal discharge for a few days for which they will be provided anticipatory guidance. During the 12-month follow-up visit, all treated women will have repeat screening with colposcopy and biopsy as needed, as well as repeat HPV-testing with provider collection. Twenty-five percent of women who have normal colposcopy results will have a random biopsy for ascertainment of cure after treatment. This may not have been performed in a routine clinical visit and may be associated with slight discomfort, but the risk to the patient will

be minimized by adequate training of clinicians, and anticipatory guidance provided to the patient. We believe that the benefit of reducing verification bias in performing these biopsies will strengthen the study results and prove a strong case for implementing this treatment method on a large scale.

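### Section 7.1 contradicts sections 3.1, 3.5.1 and 5.8 on who is examined at 12 months, and its extrapolated primary proportion has no 95% interval that allows for the 25% biopsy sample

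*Combined protocol and SAP*

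**What the plan says.** **Who is assessed at 12 months.** Section 7.1 has everyone retested for HPV, after which "those who are HPV-positive will undergo repeat colposcopy, and biopsy as indicated for abnormal results", with a random biopsy for 25% of those whose colposcopy is normal. It does not mention biopsy because of baseline CIN2/3. Section 3.1 gives repeat colposcopy to everyone treated at baseline, with "directed biopsy for those with cervical abnormalities or those with CIN2/3 at baseline". Section 5.8 says the same in substance. Section 3.5.1 states that "all treated women will have repeat screening with colposcopy and biopsy as needed".

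**How cure is defined and reported.** Section 7.1: "We will define cure as a normal biopsy result or normal colposcopy among those who do not receive a biopsy". The analysis paragraph follows: "We will report the proportion of women with no evidence of cervical dysplasia at 12-months (primary outcome) follow-up, including 95% confidence intervals". It continues: "We will extrapolate the rate of disease among those with normal colposcopy based on the rate of disease among the 25% in this group". As for how the rate from these biopsies is then used, the plan adds only that it enters the calculation of persistence. The section names no method for the interval. The only named method for an efficacy proportion is a one-sample exact test against historical controls.

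**Why the 25% sample exists.** Section 3.5.1 expects that "the benefit of reducing verification bias in performing these biopsies will strengthen the study results". Section 5.8 also gives avoidance of verification bias as the reason.

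**The concern.** There are two separate problems.

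First, the analysis section describes a different 12-month assessment from the design and procedure sections. Under 7.1 as written, a woman who is HPV-negative at 12 months has neither colposcopy nor biopsy. The cure definition needs one or the other, so she has no outcome. Women with baseline CIN2/3 would also lose systematic biopsy verification, and they are the group on which section 3.3 sizes the trial.

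Second, two rules apply to the same women. The cure definition counts every unbiopsied woman with a normal colposcopy as cured, while the extrapolation assigns some of them disease. Two analysts could therefore report different primary results. If the extrapolated figure is the one reported, part of its count is not observed but scaled up about fourfold from a small sample. A binomial interval treats that count as observed and understates the uncertainty.

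**Working it through.** **1. The schedules side by side**

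| | Colposcopy at 12 months | Biopsy because of baseline CIN2/3 |
|---|---|---|
| 3.1 | all treated | yes |
| 3.5.1 | all treated | not stated |
| 5.8 | all treated | yes |
| 7.1 | HPV-positive at 12 months only | not mentioned |

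The documents give no HPV clearance rate. If 30-70% were HPV-negative (assumed), then under 7.1 alone 0.30 × 360 = 108 to 0.70 × 360 = 252 of 360 women would have no outcome.

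**2. Inputs for the interval**

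The plan gives no figure for the precision of the primary proportion, so there is none to reproduce. Its counts do reproduce: 400 × 35% = 140, and 140 × 0.86 = 120.

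- Women seen at 12 months: 400 × 0.86 = 344 (14% loss, section 3.3) or 400 × 0.90 = 360 (10% loss, section 7.1).
- Of these, baseline CIN2/3: 120 or 126, all biopsied under 3.1 and 5.8.
- Assumed: 22% disease in that group, close to 100 − 77.2 = 22.8% from the cryotherapy rate in 3.3; 60% or 80% of the other women with normal colposcopy; 30% disease among the abnormal; hidden disease *h* of 2%, 5% or 10% among the normal.
- Denominator: all treated women seen. Schedule: that of 3.1, 3.5.1 and 5.8.

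**3. Formulas**

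With N women, N₀ unindicated normal colposcopies, m = 0.25 N₀ biopsied and disease proportion p:

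- Binomial variance: p(1−p)/N
- Two-phase variance: p(1−p)/N + (N₀/N)² × (1 − m/N₀) × h(1−h)/m
- Overstatement of cure if the definition is applied literally: 0.75 × N₀ × h / N

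**4. Two worked cases (N = 344, so 224 women without baseline CIN2/3)**

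*80% normal, h = 10%.* N₀ = 179.2 and m = 44.8. Diseased: 120 × 0.22 + 44.8 × 0.30 + 179.2 × 0.10 = 26.4 + 13.44 + 17.92 = 57.76, so p = 0.168. Binomial variance 0.000406; second term 0.521² × 0.75 × 0.09/44.8 = 0.000409. Ratio of standard errors √(0.000815/0.000406) = 1.42. Literal overstatement 0.75 × 17.92/344 = 3.9 points.

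*60% normal, h = 2%.* N₀ = 134.4 and m = 33.6. Diseased: 26.4 + 89.6 × 0.30 + 2.69 = 55.97, so p = 0.163. Binomial variance 0.000396; second term 0.000067. Ratio 1.08. Literal overstatement 0.6 points.

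**5. Simulation over all four settings (N = 344 or 360; 60% or 80% normal; 100,000 replicates each)**

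| Hidden disease | 2% | 5% | 10% |
|---|---|---|---|
| SE relative to binomial | 1.07-1.11 | 1.17-1.26 | 1.29-1.41 |
| Coverage, exact binomial interval | 93-95% | 88-92% | 85-89% |
| Coverage, two-phase interval | 94-95% | 94-95% | 93-94% |
| Literal definition overstates cure by (points) | 0.6-0.8 | 1.5-2.0 | 2.9-3.9 |

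The extrapolated estimate is unbiased to within 0.02 points. The closed-form ratios run slightly above the simulated ones because the formula ignores the fixed size of the CIN2/3 group. The random sample itself is only about 34-47 women.

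**The case against.** The sponsor can say several fair things in reply.

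- *The extrapolation is linked to the primary result.* The word persistence follows directly on the primary proportion, and 7.1 later says it will also report HPV persistence. The earlier use is therefore most naturally disease persistence, the complement of cure. This stands. A reader might infer that the extrapolation is left unconnected to the primary outcome; the text does not support that. The link is there, but loosely worded.
- *The two rules can coexist.* The planned logistic regression needs an outcome for each woman, which the cure definition supplies, while the extrapolation corrects the aggregate. This is a sensible reading, and the overstatement of cure arises only if the extrapolation is ignored. The plan does not say so, however.
- *HPV-negative women are examined.* Three sections give them colposcopy. So a reader who infers that the plan as a whole leaves them unclassified goes too far. What remains is a contradiction, and it sits in the section an analyst would follow.
- *Indicated biopsies might leak into the extrapolated rate.* A reader might worry about this, but 7.1 takes the rate from the 25%, which 3.1 and 5.8 describe as random biopsies.
- *The denominator is nearly settled.* Section 4.2 says that screen-positive women eligible for ablation form the study group. Section 3.3, though, calls CIN2/3 the outcome of interest, so one clarifying sentence is still needed.
- *The sizes are assumed, and no binomial interval is actually planned.* Both points are true. With no method named, the binomial interval is simply the likely default.

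**Conclusion.** The concern holds in two parts. Section 7.1 contradicts 3.1, 3.5.1 and 5.8 on 12-month colposcopy, and it contradicts 3.1 and 5.8 on biopsy for baseline CIN2/3. The passages must be reconciled, because followed alone 7.1 produces women whom its own definition cannot classify. Separately, the plan names no 95% interval that reflects the 25% sample.

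The second part is modest or material depending on an unknown. At 2% hidden disease a binomial interval is practically adequate; at 10% its coverage falls to about 85-89%. These figures rest on assumed rates of hidden disease, normal colposcopy and disease among abnormal findings, with all treated women as denominator.

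It would be tempting to conclude that the primary estimate is biased or that the non-inferiority result is compromised. The documents do not support either. Under the likely reading the estimate is unbiased. Under the schedule of 3.1 and 5.8 every woman with baseline CIN2/3 is biopsied, so the extrapolation does not enter the exact test in that group. If the primary denominator were that group alone, the extrapolation issue would disappear under the same schedule, which is why the denominator should be stated.

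**What to change.** 1. Reconcile 7.1 with 3.1, 3.5.1 and 5.8 on who has colposcopy and who has biopsy at 12 months. State how any woman without a 12-month colposcopy is classified, and give the denominator of the primary proportion.
2. State that the primary proportion is the extrapolated estimate, weighting the random 25% sample by the inverse of its sampling fraction. Keep the per-woman cure definition for the logistic regression and as a sensitivity analysis.
3. Report a two-phase (double-sampling) or bootstrap 95% interval in place of an ordinary binomial one.

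The extrapolation calls for no change to the exact test in women with baseline CIN2/3.

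The cost is about a paragraph of text and slightly more analysis, with no extra patients. The interval becomes somewhat wider: in the illustration its average full width is 7.7-11.1 points, against 7.1-8.6 for the exact binomial interval.
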